Appendix VI Diabetes Definitions and Other Specific Types of Diabetes

Table 1 provides a list of diabetes definitions used throughout the protocol.

Table 1. Definitions of Types of Diabetes

Term	Definition	Comment
Type 1	The destruction of the beta cells leading to an absolute deficiency of insulin resulting in diabetes.	
Type 1a: general	The autoimmune destruction of the beta cells leading to an absolute deficiency of insulin resulting in diabetes.	
Type 1a: biochemical	Identified by the presence of diabetes and any one of 4 specific diabetes autoantibodies (DAA) and fasting c-peptide < 3.7 ng/ml. (See Diabetes Autoantibody below)	
Type 1: clinical	The presence of either diabetes onset < 10 years of age AND 1. weight < the 25 th percentile for chronological age OR 2. BMI < 50 th percentile for chronological age and gender	
 • measured within one year of diagnosis • measured within one year of diagnosis
Type 2 – general	The presence of insulin resistance and beta cell dysfunction resulting in diabetes	
Type 2: biochemical	The presence of diabetes and insulin resistance and the absence of autoimmune markers	
Type 2: clinical	The presence of diabetes and a) duration of diabetes > 1 years and no insulin therapy for > 1 month without an episode of diabetic ketoacidosis or b) duration of diabetes > 6 months and never treated with insulin.	
Other Types of Diabetes	The presence of a disease or the administration of a drug that results in beta cell destruction or dysfunction or inhibits the action of insulin resulting in diabetes.	See information below for details of specific diseases
Hybrid diabetes	Biochemical evidence of more than one type of diabetes.	Biochemical evidence of both autoimmunity and insulin resistance.
Gestational Diabetes	
 • Glucose intolerance first recognized during pregnancy • Six-weeks after the pregnancy ends, the women should be reclassified as 
 ○ diabetic ○ impaired fasting glucose ○ impaired glucose tolerance ○ normoglycemic 	

Term	Definition	Comment
Autoimmunity	
 1. cytoplasmic islet cell antibodies (ICA) 2. glutamic acid decarboxylase (GAD) 3. insulin autoantibodies 4. IA-II 	
 ▪ Plasma specimen ▪ Insulin autoantibodies must be performed within 10 days of initiation of exogenous insulin therapy or the presence of insulin autoantibodies ▪ The frequency of immune markers decreases with increased duration of disease with 65% of Type 1a persons having ≥ 1 positive immune markers with duration of disease of 10 years.
Insulinopenia	A fasting plasma c-peptide < 0.8 ng/ml	
Obtained when the person is metabolically stable – defined as no episode of DKA for 1 month prior to laboratory testing. This concentration of c-peptide was chosen for the following reasons:
 
 ▪ In the Diabetes Control and Complications Trial, type 1A patients had c-peptide < 0.6 ng/ml ▪ In the Bogalusa Heart Study, the 5th percentile for fasting plasma c-peptide concentration was 0.8 ng/ml ▪ In health, non-diabetic Swedish subjects (7 to 34 years old) the 2.5th percentile was 0.7 ng/ml
Insulin Resistance	Fasting plasma c-peptide ≥ 3.7 ng./ml	This c-peptide was chosen because, in non-diabetic, health adolescents, the 95 th percentile for fasting plasma c-peptide was ≥ 3.7 ng/ml

Other Specific Types of Diabetes

Other Specific Types of Diabetes is defined as the presence of a disease or the administration of a drug that results in beta cell destruction or dysfunction or inhibits the action of insulin resulting in diabetes. Autoimmune destruction of the beta cells is excluded from this category.

Other Specific Types of Diabetes are identified by the presence of:

- Diabetes

AND

- a well defined disease or drug that results in destruction or dysfunction of the beta cells or inhibits the action of insulin.

Specific examples are:

Genetic defects of beta cell function.

- MODY 1: HNF 4 alpha
- MODY 2: Glucokinase
- MODY 3: HNF 1 alpha
- MODY 4: Insulin Promoter Factor 1
- MODY 5: HNF 1 beta
- Mitochondrial DNA
- Other

Genetic defects in insulin action

- Type A insulin resistance
- Leprechanism
- Rabson-Mendenhall Syndrome
- Lipotrophic diabetes
- Other

Disease of the exocrine Pancreas

- Pancreatitis
- Trauma/pancreatectomy
- Neoplasia
- Cystic fibrosis
- Hemochromatosis
- Fibrocalculus pancreatectomy
- Uncommon forms of immune-mediated diabetes
- “Stiff Man” Syndrome
- Anti-insulin receptor antibodies

Other genetic syndromes sometimes associated with diabetes

- Down’s Syndrome
- Klinefelter’s syndrome
- Turner’s syndrome
- Wolfram’s syndrome
- Friedreich’s ataxia
- Huntington’s Chorea
- Laurence-Moon-Biedl Syndrome
- Myotonic dystrophy
- Prophyria
- Prader-Willi syndrome
- Other

Drugs Potentially Causing Diabetes

- | | |
|---|--|
| 
 ▪ Vacor ▪ Petamidine ▪ Nicotinic acid ▪ Glucocorticoids ▪ Thyroid hormone | 
 ▪ Diazoxide ▪ Beta-adrenergic agents ▪ Thiazides ▪ Dilantin ▪ Gamma interferon |
|---|--|

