7.3. DEFINITIONS OF TERMS USED FOR TYPOLOGY

7.3.1. **Type 1 diabetes**

The progressive destruction of the beta cells leading to an absolute deficiency of insulin (see insulinopenia below) that results in diabetes.

Type 1 diabetes will be established if all diabetes autoantibodies (DAA – see autoimmunity below) are negative and any of the following are present:

- a. Fasting C-peptide < 0.8 ng/ml;

Or

- b. Diagnosis of diabetes was made when the subject was < 10 years of age with a weight < the 25th percentile for chronological age or BMI < 50th percentile for chronological age;

Or

- c. Duration of diabetes > 1 year and if daily administration of insulin is stopped it results in DKA.

7.3.2. **Type 1A diabetes (general)**

The autoimmune destruction of the beta cells leading to an absolute deficiency of insulin resulting in diabetes.

7.3.3. **Type 1A diabetes (biochemical)**

The presence, in plasma, of any specific diabetes autoantibody and a fasting C-peptide < 3.7 ng/ml. These markers include antibodies to glutamic acid decarboxylase (GAD), IA-2, and insulin autoantibodies (IAA) measured by radioassay and cytoplasmic islet cell antibodies measured by immunofluorescence (ICA). The frequency of the presence of immune markers decreases with increased duration of disease with only 65% of Type 1A patients having one or more positive immune markers with duration of disease of 10 years^{33,34}.

7.3.4. **Type 2 diabetes (general)**

The presence of insulin resistance (see insulin resistance) and beta cell dysfunction resulting in diabetes. Type 2 diabetes will be established if one of the following exists:

- a. Duration of diabetes > 1 year and no insulin therapy for > 1 month without an episode of diabetic ketoacidosis

Or

- b. Duration of diabetes > 6 months and never treated with insulin.

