7.4.2. Incident algorithms

The incident algorithm will be used to establish type of diabetes for incident cases. This algorithm displays use of data collected from the In-Person Visit Module. For incident cases for whom the In-Person Visit is not available, typology will proceed using data collected from the Medical Record Module or the Core Form. (See Data Collection, Section 5, for descriptions)

Algorithm - Incident cases– Information Available from In-Person Visit

- a. Type 1A diabetes will be established if any of the three DAA (GAD, IAA, and IA-2) is positive and the fasting C-peptide is < 3.7 ng/ml.
- b. Type 2 diabetes will be established if the DAA titers are all negative and the fasting C-peptide is ≥ 3.7 ng/ml.
- c. Hybrid diabetes is established if any DAA are positive and fasting C-peptide is ≥ 3.7 ng/ml.
- d. DAA negative participants ≥ 8 years of age at their baseline examination who have a fasting C-peptide concentration < 3.7 ng/ml will undergo additional DAA and SCP testing as described in Section 5 – Data Collection. These data will be used to classify participants in the following manner.
 - i. If any subsequent DAA become positive, a classification of ‘type 1A diabetes’ will be made.
 - ii. If all subsequent DAA remain negative and one or more fasting C-peptide concentrations < 3.7 ng/ml, classification will be made in the following manner. Clinical characteristics and SCP data collected over time will be compared to the same data generated in the sub-group of the incident cases classified as type 1A or all incident cases classified as type 2 diabetes. Where the data matches these groups, a classification of type 1 or type 2 will be made.
 - iii. In remaining participants who cannot be classified by the method described in ‘ii’ (above), clinical definitions of the types of diabetes found in appendix VI will be used to classify participants as type 1 and type 2 diabetes.

- iv. The remaining participants who cannot be classified by the method described in 'iii' (above) will be classified as untypeable.

Algorithm - Incident cases – Information from In-Person Visit Not Available

Among incident cases for which the In-person Module is not available, information may be available from the Core Form and/or Medical Record review. The following information will be obtained: 1) DAA and plasma C-peptide tests and the laboratory at which these tests were performed, and 2) limited clinical data.

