7.4.3. Prevalent algorithms

The prevalent algorithm is used to establish the type of diabetes for prevalent cases. This algorithm displays use of data collected from the In-Person Visit Module. For prevalent cases for whom the In-Person Visit is not available, typology will proceed using data collected from the Core Form. (See Data Collection, Section 5, for descriptions)

Algorithm - Prevalent Cases – Information Available from In-Person Visit

[figure not shown]
- a. Type 1A diabetes will be established if any of the three DAA (GAD, IAA, and IA-2) are positive and a fasting C-peptide < 0.8 ng/ml (see appendix VII).
- b. Type 1 diabetes will be established if all DAA are negative and a fasting C-peptide < 0.8 ng/ml;
- c. Type 2 diabetes will be established if *all* DAA titers are negative and a fasting C-peptide is ≥ 3.7 ng/ml.
- d. Hybrid diabetes is established if any DAA is positive and fasting C-peptide ≥ 3.7 ng/ml.
- e. DAA positive patients ≥ 8 years of age at their baseline examination who have a fasting C-peptide ≥ 0.8 ng/ml and < 3.7 ng/ml will undergo a single SCP test. These data will be used to type the participants in the following manner:
 - i. The clinical and SCP data will be compared to the same data generated in the sub-groups of the incident cases classified as type 1A, hybrid diabetes and type 2.

[figure not shown]
- ii. The clinical and SCP data will be compared to the same data generated in the prevalent cases classified as hybrid diabetes and prevalent cases that are untypeable.
- f. DAA negative patients ≥ 8 years of age at their baseline examination who have a fasting C-peptide ≥ 0.8 ng/ml and < 3.7 ng/ml will undergo a single SCP test. These data will be used to type the participants in the following manner:
- i. The SCP data will be compared to the same data generated in the sub-groups of the incident cases classified as type 1A diabetes and type 2 diabetes. When the data is comparable to the sub-groups, a classification of type 1 or type 2 will be made.
 - ii. In the remaining participants who cannot be classified by the method described in ‘i’ (above), the clinical definitions of the types of diabetes found in appendix VI will be used to classify participants as type 1 and type 2 diabetes.
 - iii. The remaining participants who cannot be classified by the method described in ‘ii’ (above) will be classified as untypeable.

Algorithm- Prevalent cases – Information Available from In-Person Visit Not Available

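### Appendix VI's clinical type 1 definition omits the age-independent criteria of 7.3.1, so unresolved antibody-negative cases with onset at 10 or older cannot become type 1 at the fallback step

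*Protocol*

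**What the plan says.** Section 7.3.1 says antibody-negative type 1 is established by any one of three routes:

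- (a) "Fasting C-peptide < 0.8 ng/ml", with no age limit;
- (b) "Diagnosis of diabetes was made when the subject was < 10 years of age with a weight < the 25th percentile", or a BMI below the 50th percentile;
- (c) "Duration of diabetes > 1 year and if daily administration of insulin is stopped it results in DKA", with no age limit.

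The incident algorithm (7.4.2) sends antibody-negative participants aged 8 or over with C-peptide below 3.7 ng/ml to step d. There they may become type 1A on later antibody positivity (d.i), or type 1 or 2 by comparing clinical and stimulated C-peptide data with typed incident cases (d.ii). For the remainder, step d.iii says that "clinical definitions of the types of diabetes found in appendix VI will be used to classify participants as type 1 and type 2 diabetes". Anyone still unclassified is untypeable (d.iv).

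The prevalent algorithm (7.4.3) has a direct step b: "Type 1 diabetes will be established if all DAA are negative and a fasting C-peptide < 0.8 ng/ml". Antibody-negative cases aged 8 or over with C-peptide from 0.8 to below 3.7 go to a stimulated C-peptide comparison (f.i). For those left, step f.ii says that "the clinical definitions of the types of diabetes found in appendix VI will be used to classify participants as type 1 and type 2 diabetes".

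In Appendix VI, Table 1, the row 'Type 1: clinical' begins "The presence of either diabetes onset < 10 years of age AND" and continues with weight below the 25th percentile, OR, BMI below the 50th. The row 'Type 2: clinical' has two routes: more than a month off insulin without DKA after more than a year of diabetes, or "duration of diabetes > 6 months and never treated with insulin". Neither has an age limit.

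**The concern.** The fallback steps name Appendix VI, not 7.3.1. Both clinical type 2 routes of 7.3.4 appear in full in Appendix VI. Of the three type 1 routes in 7.3.1, only the one limited to diagnosis before age 10 is in the clinical type 1 row. Route (c) is a clinical criterion and would be expected there, but it is absent. The fallback therefore offers type 2 at every age and type 1 only for onset before 10.

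Estimating prevalence and incidence by type is primary aim (a) in section 1.2, and classification is primary aim (b). Any loss runs one way, out of the type 1 numerator, and falls in the 10-19 age band, where telling type 1 from type 2 is hardest.

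The type 1 row is also ambiguous. 'Either', 'AND' and 'OR' appear in one sentence without brackets, so two analysts could type the same adolescent differently.

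**Working it through.** **1. The passages side by side (antibody-negative, onset at 10 or older)**

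| Type 1 route | 7.3.1 | Prevalent algorithm before fallback | Incident algorithm before fallback | Appendix VI clinical row |
|---|---|---|---|---|
| Fasting C-peptide < 0.8 | yes (a) | yes (step b) | no direct step | no |
| Low weight or BMI | only if diagnosed before 10 (b) | no | no direct step | only if onset before 10 |
| DKA when insulin stopped, duration > 1 year | yes (c) | no | no direct step | no |
| Stimulated C-peptide comparison | not listed | yes (f.i) | yes (d.ii, with clinical characteristics) | no |
| Later antibody positivity (type 1A) | not listed | no | yes (d.i) | no |

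**2. Reachable labels for onset at age 14, antibody-negative**

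Reading A: onset < 10 AND (weight < 25th OR BMI < 50th). Reading B: (onset < 10 AND weight < 25th) OR BMI < 50th.

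- Whole algorithm, incident or prevalent, either reading: type 1, type 2 and untypeable are all reachable.
- Fallback step alone, reading A: type 2 or untypeable only.
- Fallback step alone, reading B: type 1 is also reachable.

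Reading A is the natural one. It agrees with 7.3.1 (b), and the numbered layout of the Appendix VI row pairs weight with BMI under the age condition.

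**3. Two cases where the passages give different answers (reading A)**

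- Incident, onset at 12, C-peptide 0.5 ng/ml, antibodies stay negative, no match at d.ii, continuously on insulin. By 7.3.1 (a), type 1. By 7.4.2 with Appendix VI, untypeable. A prevalent case with the same results is type 1 at step b.
- Prevalent, onset at 12, C-peptide 1.5 ng/ml, no match at f.i, meets 7.3.1 (c), and no period of more than a month off insulin without DKA. By 7.3.1, type 1. By f.ii with Appendix VI, untypeable.

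**4. Scale**

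Inputs are the centre rows for ages 10-19 in Tables V-4 and V-5.

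- Type 1: 46 + 89 + 13 + 45 + 70 + 85 = 348 a year.
- Type 2: 21 + 40 + 17 + 9 + 22 + 25 = 134 a year.
- Check: 348 + 134 = 482, the 10-19 count in Table 6-2. With ages 0-9 (273 and 30) the totals are 621 and 164, as printed, and 785 together.
- Type 1 rate at 10-19, with the Table 6-2 denominator: 348 / 2,539,670 = 13.70 per 100,000.

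The share f of these 348 that stays unresolved up to the fallback, and so leaves type 1, is not in the document. Over an assumed range, cases lost = f × 348 and rate = (348 − f × 348) / 2,539,670:

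| f (assumed) | Cases leaving type 1 a year | Type 1 rate per 100,000 |
|---|---|---|
| 1% | 3.5 | 13.57 |
| 5% | 17 | 13.02 |
| 10% | 35 | 12.33 |
| 20% | 70 | 10.96 |

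For comparison, one year's Poisson 95% half-width on 348 cases is 1.96 / √348 = 10.5%. The loss passes one year's sampling error only if f is above about 10%.

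Prevalent counts are not used in this step, because their age bands are current age and not age at onset.

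**The case against.** A reader might infer that antibody-negative adolescents in general can only become type 2 or untypeable. The documents do not support that. Prevalent step b makes C-peptide below 0.8 type 1 at any age, d.ii and f.i can assign type 1, and d.i can assign type 1A. Only the residue left after those steps is affected.

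A reader might also infer that type 2 is inflated by the same number. At f = 5% that would be 17.4 / 134 = 13%, but only if every affected case were called type 2. Clinical type 2 needs time off insulin without DKA, or no insulin at all. A case continuously on insulin meets neither and becomes untypeable, leaving the type 2 count unchanged.

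The protocol also has safeguards. Unclassified participants are followed and may be reassigned (7.2 a), clinical definitions are to be redefined at study end (7.2 b), and the algorithm may be modified (7.4.1). These stand in part. However, 7.2 b re-types patients with clinical data only, not those with in-person antibody and C-peptide results, and neither 7.2 a nor 7.4.1 says which of the two type 1 definitions governs.

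Finally, 'either' may simply pair with the weight and BMI items, so it does not prove that a branch was dropped. That is fair. The finding rests on the mismatch with 7.3.1, not on that word. Nor does reading B rescue the text, because it departs from 7.3.1 (b).

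**Conclusion.** Wrong as written, but narrow. Section 7.3.1 and the fallback through Appendix VI give different types to the same antibody-negative case with onset at 10 or older once the earlier steps have failed to resolve it. The likely effect is an understatement of type 1 at ages 10-19, mostly through cases becoming untypeable. Bias in the type-specific rates is possible, not demonstrated.

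The size is about 3.5 incident cases a year for each 1% of the 348 left at the fallback. It rests on the planning counts, on reading A, and on an unstated residual share. That share cannot be assumed negligible: the matching at d.ii and f.i has no stated rule, and the stimulated C-peptide test needs separate consent (11.6). The figure is also a ceiling on what reconciliation could recover, since only cases that meet the criteria finally adopted would move back to type 1.

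**What to change.** 1. Reconcile 7.3.1, 7.4.2, 7.4.3 and Appendix VI so that one set of type 1 criteria governs d.iii and f.ii. Either the Appendix VI row is aligned with 7.3.1, or the two steps point to the section that governs, or 7.3.1 is changed. Which criteria apply is for the investigators to decide.
2. In the same edit, settle why prevalent step b has a direct type 1 step for negative antibodies with C-peptide below 0.8 and the incident algorithm has none, and state whether the difference is intended.
3. Rewrite the 'Type 1: clinical' row with brackets or separate lines so that the either/AND/OR wording has one reading.
4. Re-run the fallback typing for cases already classified, using the data already collected, and report by age band how many reached the fallback and what label each received.

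The cost is one table row or two cross-references, plus a re-run of the typing program. One caution: if criterion (c) is kept, the information may be missing for some incident cases, because medical record review in 5.7.1 ends six months after diagnosis while (c) concerns diabetes of more than a year. The re-run should count such cases as not assessable for (c), not as failing it.
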